8.2.22. Signs and Symptoms of Invasive Aspergillosis

Targeted physical examinations/clinical evaluations of signs and symptoms of IPA will be listed.

8.2.23. Chest CT Scan

Results from the chest CT scans will be listed.

9. Analysis Of Pharmacokinetics

As planned in the protocol population PK analysis will be done and reported in a separate report. This SAP does not include the specifics of PopPK which will be outlined in a separate SAP. The population PK analysis will include the PK data in this study SCY078-206.

9.1. PK Sampling Schedule

PK testing for the determination of ibrexafungerp will be conducted for all subjects. Blood samples for ibrexafungerp PK testing will be collected predose on Treatment Days 1, 3, 7 and 14, approximately within 1 hour before dosing, and on Treatment Days 1, 7 and 14 at 2-4 hours and at 6-8 hours after dosing. Voriconazole level determination will also be performed for all study subjects predose on Treatment Days 1, 3, 7 and 14, approximately within 1 hour before dosing, and on Treatment Days 1, 7 and 14 at 2-4 hours and at 6-8 hours after dosing.

9.2. PK Concentration

The summary statistics of plasma concentrations will be presented per treatment (ibrexafungerp, voriconazole), PK Day (Pre-first dose, Day 1, Day 7 and Day 14) and by time interval (pre-dose, 2-4 and 6-8 hours post dose), and BLQ concentration values should be set to 0. All concentration values presented as BLQ and the number of BLQs (ie, n below the lower limit of quantitationLLOQ) for each time interval will be listed as reported.

10. Safety

The population used for safety analyses will be the Safety Population. Safety will be assessed on the basis of AEs, clinical laboratory data, vital signs, ECG parameters and physical examinations

10.1. Extent of Exposure

Extent of exposure will be considered separately for study drug (ibrexafungerp or ibrexafungerp placebo) and Voriconazole.

For study drug, duration of treatment (weeks) will be calculated as:

$$\text{Duration of treatment (weeks)} = (\text{Date of last dose} - \text{Date of first dose} + 1)/7.$$

In addition, the number of days of treatment will also be calculated, taking into account any dose interruptions.

For the ibrexafungerp arm, the total dose in mg will be calculated from the sum of the number of tablets taken from the study drug dispensing log.

In addition, average daily dose will be calculated as the total dose in mg, divided by the duration of treatment in days.

Duration of treatment, number of days of treatment, total dose and average daily dose will be summarized for the Safety Population.

For Vorinconazole, duration of treatment (weeks) will be calculated as:

$$\text{Duration of treatment (weeks)} = (\text{Date of last dose} - \text{Date of first dose} + 1)/7.$$

In addition, the number of days of treatment will also be calculated, taking into account any dose interruptions.

Duration of treatment and number of days of treatment will be summarized for the Safety Population.

10.2. Treatment Compliance

For study drug, compliance (%) will be calculated as:

$$\text{Compliance (\%)} = 100 * (\text{Number of tablets taken} / \text{Expected number of tablets taken}),$$

where the number of tablets taken will be calculated from the sum of the number of tablets taken from the study drug dispensing log, and the expected number of tablets taken will be based on the first and last dose dates, accounting for the loading doses.

Compliance will be summarized for the Safety Population. In addition, compliance will be summarized according to the categories:

- <80%
- 80% to <120%
- ≥120%.

10.3. Adverse Events

Adverse events will be coded into SOCs and PTs using the MedDRA 26.0 .

If the relationship to a study drug is missing then in the summary tables the AE will be classified as related. Similarly, missing severity will be classified as severe in the summary tables.

Treatment-related AEs will be those with relationship to either ibrexafungerp or voriconazole of related.

Summary tables of AEs will be based on treatment emergent adverse events (TEAEs).

A TEAE is defined as any event not present prior to the initiation of the study treatment, or any event already present which worsens either in intensity or frequency following the exposure to the study treatment.

AEs with incomplete start dates will be considered as TEAE if:

- Day and month are missing and the year is equal to or after the year of the first dose date
- Day is missing and the year is after the year of the first dose
- Day is missing and the year is equal to the year of the first dose date and the month is equal to or after the month of the first dose date
- Year is missing
- Complete start date is missing.

For summaries by SOC and PT, a subject will be counted once at the SOC level and once at each PT within the SOC level. For summaries by SOC, PT and maximum severity, a subject will be counted once at the highest severity for which an event occurred at the SOC level and the highest severity for each unique PT within that SOC level. Therefore, subjects may only contribute once to each PT and once to each SOC level.

An overall summary of TEAEs will be provided showing the number and percentage of subjects reporting TEAEs, treatment-related TEAEs, TEAEs with severe severity, TEAEs leading to withdrawal of study treatment, serious TEAEs and treatment-related serious TEAEs, TEAEs leading to Death.

The following TEAE tables will also be provided:

- A summary of TEAEs overall and by SOC and PT
- A summary of treatment-related TEAEs overall and by SOC and PT
- A summary of TEAEs by maximum severity, overall and by SOC and PT
- A summary of TEAEs leading to withdrawal of study treatment, overall and by SOC and PT
- A summary of serious TEAEs, overall and by SOC and PT
- A summary of treatment-related serious TEAEs, overall and by SOC and PT
- A summary of TEAEs leading to Death, overall and by SOC and PT

The above summaries will show the number and percentage of subjects reporting events in the respective categories. All summaries will be by treatment group. Only the TEAEs will be included in the summary tables, however all AEs will be included in the listings.

Listings will be provided for all AEs, AEs leading to study treatment withdrawal and SAEs. TEAEs will be flagged in the listings.

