13.3 Study Drug

Study drug, SCY-078 250-mg and SCY-078 250-mg matching placebo tablets will be provided by the Sponsor. Standard of care (SOC) voriconazole (IV and oral) will be provided by the study site's pharmacy. In extenuating circumstances when the site's pharmacy is not able to provide the SOC voriconazole, the Sponsor will assist in obtaining it.

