15.25 Study Drug Dosing

Study drug doses (oral SCY-078 or oral SCY-078 matching placebo) will be administered daily to subjects from Baseline (Treatment Day 1) through EoT. The study drugs will be administered in a blinded fashion. Treatment may be given on an inpatient or outpatient basis, as needed, and for as long as is clinically indicated, at the investigator's discretion, but in no event for more than a total of 13 weeks (i.e. 91 days) of study drug treatment.

For subjects who are unable to take oral medications, SCY-078 tablets may be crushed and administered with approximately 8 oz./240 mL of water via an NG or PEG tube. The tube should be flushed with water before and after drug administration.

Oral SCY-078 will be administered preferably with meal.

Loading dose:

• The first 4 doses of oral SCY-078 500 mg will be administered BID, approximately every 12 hr (total dose of 1000 mg per day for 2 days)

Maintenance dose:

• Starting with the 5th dose of oral SCY-078 500 mg the subsequent doses will be administered QD (total dose of 500 mg per day). The 5th dose may be administered within 12 to 24 hrs of the 4th dose, to allow for adjustment to a QD dose regimen that is the most convenient for the patient (either AM or PM). Subsequent doses should be administered approximately 24 hr apart.

The dose of SCY-078 may be adjusted for subjects who are randomized after the interim PK analysis. Until a decision to adjust the dose is made based on data from this analysis, subjects will continue receiving SCY-078 500 mg doses as described above.

If after interim PK analysis the daily dose is changed from 500 mg to 750 mg the dosing instructions will be the same but 500mg dose will be substituted by 750 mg dose. Specifically, the loading dose will be oral SCY-078 750 mg BID for 4 doses, followed by maintenance dose of 750 mg QD subsequently.

For subjects who are intolerant of SCY-078 due to gastrointestinal (GI) related conditions such as clinically significant nausea or diarrhea, the following dose administration adjustments are allowed:

- Each tablet of SCY-078 may be administered every 10-20 min rather than all at once.
- The daily dose during the maintaining phase (after the first 4 loading doses) can be changed from QD to BID, administering 250 mg of SCY-078 (one tablet) approximately every 12 hr, preferably with a meal (total dose of 500 mg per day).

SCYNEXIS, Inc.	IND #107,521
PROTOCOL SCY-078-206	Version 5.0

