17.8 Causality Assessment

The investigator will assess causality (i.e., whether there is a reasonable possibility that the study drug caused the event) for all AEs and SAEs. The relationship will be characterized using the following classification:

- Related: The temporal relationship of the AE with the study drug makes causality possible and cannot be due to another cause such as other drugs, a surgical intervention or an underlying disease.
- Not related: The temporal relationship of the AE with the study drug makes causality improbable and can be due to another cause such as other drugs, a surgical intervention or an underlying disease.

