- q. Blood samples for voriconazole level determination will be performed for all study subjects at a central laboratory. For the first 20 randomized subjects, blood PK samples will be collected predose on Treatment Days 1, 3, 7 and 14, approximately within 1 hour before dosing and at 2-4 hours and 6-8 hours after dosing on Treatment Days 1, 7 and 14. The PK data from the first 20 subjects will be assessed in an interim PK analysis. For subjects subsequently randomized, blood PK samples will be collected predose on Treatment Days 1, 3, 7 and 14, approximately within 1 hour before dosing, and on Treatment Days 1, 7 and 14 at 4-8 hours after dosing. The time of dosing and sample collection must be recorded in the eCRF.
- r. Blood samples for voriconazole level determination to be collected as needed (e.g., within 7 days after making any dose adjustment or evidence of toxicity) and sent to the central lab.
- s. Samples for ibrexafungerp PK will be collected predose on Treatment Days 1, 3, 7 and 14, approximately within 1 hour before dosing, and at 2-4 hours and 6-8 hours after dosing on Treatment Days 1, 7 and 14.. The time of dosing and sample collection must be recorded in the eCRF and on the subject’s medical record.
- t. All randomized subjects will receive either ibrexafungerp + voriconazole or ibrexafungerp placebo + voriconazole.
- u. For non-hospitalized patients only.

Table 2 Schedule of Treatment Visits and Procedures for Days 42 and 84 (Study SCY-078-206)

PROCEDURE	Visit/contact	Visit/contact
Visit	Survival	Survival
	Day 42	Day 84
Days (allowable window)	± 2	± 4
Assessment of treatment outcome	X	X
Subject Status (alive/ deceased)	X	X
Karnofsky Score	X	X

4. Endpoints

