4.1. Primary Endpoint

- Frequency of treatment-emergent adverse events (TEAEs), drug-related adverse events (AEs), discontinuations due to AEs and deaths.

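### SAP 10.3 reports related adverse events only as related to either drug; because both arms take voriconazole, separate by-drug rows are needed to show attribution to ibrexafungerp

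*SAP*

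**What the plan says.** The primary endpoint, in SAP 4.1 and Protocol 10.1, has four components: "Frequency of treatment-emergent adverse events (TEAEs), drug-related adverse events (AEs), discontinuations due to AEs and deaths". It does not say which drug 'drug-related' refers to.

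SAP 10.3 supplies the working definition: "Treatment-related AEs will be those with relationship to either ibrexafungerp or voriconazole of related". Three outputs rest on it: the related lines of the overall TEAE summary, the related-TEAE table by SOC and preferred term, and the related serious TEAE table. No table restricted to ibrexafungerp-related or to voriconazole-related events is planned. The same section counts an AE as related when its relationship to a study drug is missing.

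On treatment, the notes to the SAP 3.8 schedule state: "All randomized subjects will receive either ibrexafungerp + voriconazole or ibrexafungerp placebo + voriconazole". The randomised difference is therefore ibrexafungerp against its placebo.

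On causality, Protocol 17.8 states: "The investigator will assess causality (i.e., whether there is a reasonable possibility that the study drug caused the event) for all AEs and SAEs". For exposure, the SAP does split the drugs: "Extent of exposure will be considered separately for study drug (ibrexafungerp or ibrexafungerp placebo) and Voriconazole" (SAP 10.1).

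**The concern.** The drug-related component is the only one of the four that depends on the investigator's attribution. Its natural use is to show which events investigators ascribe to the tablet whose addition is being tested. Under the union rule, a subject with a voriconazole-attributed event is already in the any-related row, so an ibrexafungerp-attributed event in that subject leaves the row unchanged. The same happens inside a SOC or preferred term to which both drugs contribute. Liver tests are a plausible example: Protocol 8.1 reports transient liver-test increases with SCY-078, and Protocol 15.17 requires transaminase and bilirubin monitoring because of the voriconazole label.

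At stake is whether a reader of the summary tables can separate attribution to the new drug from attribution to a background drug that both arms share.

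**Working it through.** The plan gives no related-AE rates, and SAP 3.6 says there is no formal sample size calculation, so there is no stated figure to reproduce. All rates below are assumptions.

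**Notation, per arm**
- a1, a0: proportion of subjects with an AE attributed to the tablet (ibrexafungerp arm, placebo arm)
- v: proportion with an AE attributed to voriconazole, taken as equal in both arms
- o1, o0: proportion with both

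**Formula.** Pooled proportion = a + v − o. Since v cancels between arms:

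Pooled risk difference = (a1 − a0) − (o1 − o0)

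The difference shrinks only to the extent that overlap is greater in the ibrexafungerp arm. Under independence o = a × v, so the pooled difference is (a1 − a0)(1 − v).

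**Effect of v under independence, a1 = 0.40, a0 = 0.10**

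| v | Pooled rates | Risk difference | Risk ratio |
|---|---|---|---|
| 0 (tablet only) | 40% vs 10% | 0.30 | 4.0 |
| 0.1 | 46% vs 19% | 0.27 | 2.42 |
| 0.3 | 58% vs 37% | 0.21 | 1.57 |
| 0.5 | 70% vs 55% | 0.15 | 1.27 |

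Worked line at v = 0.3: 1 − 0.6 × 0.7 = 0.58 and 1 − 0.9 × 0.7 = 0.37; 0.58 − 0.37 = 0.21.

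Other tablet rates at v = 0.3, with a0 = 0.10:
- a1 = 0.30: the difference goes from 0.20 to 0.14 and the ratio from 3.0 to 1.38.
- a1 = 0.50: the difference goes from 0.40 to 0.28 and the ratio from 5.0 to 1.76.

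**Effect of the overlap pattern, a1 = 0.40, a0 = 0.10, v = 0.3**

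| Pattern (same in both arms) | o1, o0 | Pooled rates | Risk difference | Risk ratio |
|---|---|---|---|---|
| Disjoint | 0, 0 | 70% vs 40% | 0.30 | 1.75 |
| Independent | 0.12, 0.03 | 58% vs 37% | 0.21 | 1.57 |
| Full overlap | 0.30, 0.10 | 40% vs 30% | 0.10 | 1.33 |

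The ratio moves towards 1 in all three patterns. The difference does not move at all in the first.

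**In subjects.** SAP 3.4 gives about 11 per group. The tablet-only difference is 11 × 0.30 = 3.3 subjects. Pooled, it is 11 × 0.21 = 2.3 under independence and 11 × 0.10 = 1.1 under full overlap.

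**Protocol terminology**
- Voriconazole excluded: Protocol 13.3 says "Study drug, SCY-078 250-mg and SCY-078 250-mg matching placebo tablets will be provided by the Sponsor" and calls voriconazole standard of care. Protocol 15.25 says "Study drug doses (oral SCY-078 or oral SCY-078 matching placebo) will be administered daily".
- Voriconazole included: the synopsis describes it under its study-drugs heading. Section 13.1.2 defines study treatment as voriconazole plus SCY-078 or placebo. Appendix A (22.1.1) bars any antifungal other than the study drug, which makes sense only if voriconazole is covered.
- Unspecified: section 19.6.2, which governs the safety analysis, plans summaries by relationship to treatment.

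These sections do not settle which drug the drug-related component means.

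**The case against.** The strongest defence is that the pooled count suits the objective. The trial compares coadministration with placebo plus voriconazole, and Protocol 19.8.2 wants to check that neither drug alters the other's exposure. If ibrexafungerp raised voriconazole-attributed toxicity, the pooled row would catch it and a tablet-only row would not. With v at 0.5 in the ibrexafungerp arm and 0.3 in the placebo arm, and the same tablet rates, the pooled difference is (1 − 0.6 × 0.5) − (1 − 0.9 × 0.7) = 0.70 − 0.37 = 0.33, above the tablet-only 0.30. This stands, and it is why the pooled row should remain.

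Two stronger readings are tempting, and the documents support neither.

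- **That the SAP departs from the protocol without declaring it.** Protocol 17.8 read with 13.3 and 15.25 invites this, and SAP section 12 declares no deviations. But the protocol's usage is mixed, and related to either drug is a reasonable way to carry out the relationship-to-treatment wording of section 19.6.2.
- **That a safety signal is hidden from the primary endpoint.** Total TEAEs, discontinuations due to AEs and deaths do not use attribution and are shown by arm. The SOC and preferred-term tables still count a gastrointestinal event in a subject who already has a voriconazole-attributed visual event. All AEs are listed, and with about 22 subjects the attribution may be recoverable there, although the SAP does not say that the listings show relationship by drug. The analysis is descriptive, so no test is affected.

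None of this replaces a by-drug summary, and none is planned.

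**Conclusion.** The point holds as a reporting gap in one of the four primary-endpoint components. As planned, the any-related row, and any SOC or preferred-term row where both drugs are blamed, cannot separate attribution to ibrexafungerp from attribution to voriconazole.

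The size is conditional. With equal v and independence, the risk difference is multiplied by 1 − v. With disjoint groups it is unchanged, and with full overlap in the example it falls from 30 to 10 points. The rates, the equality of v and the overlap pattern are all assumptions. The conclusion that by-drug rows are needed does not depend on them; it follows from the definition and the shared background drug.

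**What to change.** In SAP 10.3:

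1. Keep the related-to-either row and tables.
2. Beside them, add rows in the overall summary, and SOC and preferred-term tables, for TEAEs related to ibrexafungerp/placebo and for TEAEs related to voriconazole. Do the same for serious TEAEs.
3. Apply the missing-relationship rule to each drug separately, so that a blank voriconazole field does not make an event count as related to the tablet.
4. State how the three versions map to the drug-related component of the primary endpoint.

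The cost is a few extra rows and tables. The SAP's definition implies that relationship is recorded for each drug, so no new data collection should be needed. The case report form is not among the documents, so this should be confirmed before the tables are programmed.

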19.6.2 Safety Analyses

All safety analyses will be conducted using the ITT/safety population; all safety variables will be listed.

The incidence and severity of TEAEs and SAEs and their relationship to treatment will be summarized. AEs will be coded using the Medical Dictionary for Regulatory Activities (MedDRA) Version 19.1 or higher and presented by system organ class and preferred term.

Early discontinuation of study drug treatment will be presented and will include the reasons for and timing of such discontinuations.

Prior and concomitant medications will be summarized; medications will be classified based on the World Health Organization's Drug Dictionary terminology.

Abnormal physical examinations will be listed. Laboratory evaluations will be summarized as observed values and changes from Baseline; shifts with respect to the laboratory reference range will be summarized. Events of clinical interest will be summarized.

Vital signs and ECG evaluations will be summarized as observed values and changes from Baseline.

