19.7.2 Efficacy Analyses

The secondary efficacy endpoint, the percentage of subjects with successful Global Response (Complete Response or Partial Response) at EoT, Day 42 and Day 84 as determined by the DRC and the Principal Investigator will be presented by treatment group along with an estimate of the difference between treatment groups. The response rate will be calculated for each treatment group as the number of successes divided by the total number of patients (success + failure + indeterminate). The difference in response rates between treatments will be presented along with a 95% confidence interval (CI), calculated using the method of Miettinen and Nurminen. The secondary analysis of ACM at Day 42 and Day 84 will be presented by treatment group along with an estimate of the difference between treatment groups. In addition, a Kaplan Meier plot will be produced to summarize overall survival over time.

The remaining secondary and exploratory endpoints will be summarized by treatment group.

Provided sufficient data are available to allow meaningful presentation, results of the key efficacy parameters will also be presented by baseline *Aspergillus* species; by baseline minimum inhibitory concentration (MIC) and minimal effective concentration (MEC) for voriconazole and SCY-078, respectively; and by baseline neutropenia and persistent neutropenia at Week 2.

Considering the exploratory nature of this study, further analysis may be defined in the statistical analysis plan, as deemed appropriate. For example, if the data are heterogeneous within this randomized study, attempts may be made to match patients across the treatment groups on key disease criteria, if sufficient data are available, to better understand the comparability of the randomized groups.

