3.1. Primary Objective

To evaluate the safety and tolerability of the coadministration of ibrexafungerp and voriconazole compared with coadministration of ibrexafungerp placebo and voriconazole in the treatment of invasive pulmonary aspergillosis (IPA).

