8.2.3. All-Cause Mortality

All-cause mortality is defined as all deaths following the first dose of study drug, regardless of attribution. The total number of deaths by Day 42 and Day 84 and relationship to the fungal infection will be summarized. The difference in mortality rates between treatments will be presented along with a 95% CI calculated using the method of Clopper-Pearson.

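### Three of the four primary safety components get only per-arm counts, although the primary objective compares the arms; only deaths have a planned difference, with an interval method that does not apply to one

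*SAP*

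**What the plan says.** SAP 3.1 states a comparative primary objective: "To evaluate the safety and tolerability of the coadministration of ibrexafungerp and voriconazole compared with coadministration of ibrexafungerp placebo and voriconazole". SAP 4.1 gives the primary endpoint as "Frequency of treatment-emergent adverse events (TEAEs), drug-related adverse events (AEs), discontinuations due to AEs and deaths", which is four components.

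For adverse events, SAP 10.3 lists an overall summary and a set of tables by system organ class and preferred term, and then says: "The above summaries will show the number and percentage of subjects reporting events in the respective categories. All summaries will be by treatment group". Protocol 19.6.2 is equally descriptive: "The incidence and severity of TEAEs and SAEs and their relationship to treatment will be summarized". Neither section mentions a difference between arms or an interval.

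Deaths are treated in two places. SAP 10.3 has a table of TEAEs leading to death, with counts only. SAP 8.2.3, in the efficacy chapter, says "All-cause mortality is defined as all deaths following the first dose of study drug, regardless of attribution", counts those deaths by Day 42 and Day 84, and adds: "The difference in mortality rates between treatments will be presented along with a 95% CI calculated using the method of Clopper-Pearson". Protocol 19.7.2 agrees that there should be a contrast: "ACM at Day 42 and Day 84 will be presented by treatment group along with an estimate of the difference between treatment groups". SAP 8.2.2 adds Kaplan-Meier survival at both days with 95% CIs.

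SAP 8.1, 8.2.5, 8.2.10 and 8.2.11 plan between-arm differences with 95% CIs for Global Response, serum GMI targets, beta-D-glucan targets and PCR conversion.

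**The concern.** The plan gives an estimate with uncertainty to secondary and exploratory rates, but not to three of the four components of its own primary endpoint. An n (%) table places the arms side by side; it does not estimate the comparison that the objective names or show how imprecise that comparison is.

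Precision matters more since enrolment stopped at 22 of a planned 60 (SAP 12). At this size, similar percentages in the two arms say little about whether the true rates are similar, and nothing in SAP 10.3 makes that visible. The data are meant to inform later studies (SAP 3.6), and a planner there needs the range as well as the observed counts.

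**Working it through.** **Inputs**
- Arm size: about 11 per group (SAP 3.4, with 22 randomized in SAP 11 and 12). SAP 3.7 says about 10 per arm, so both are shown. The planned size was 30 per arm (protocol 11.2).
- Interval method: Miettinen-Nurminen, which protocol 19.7.2 names for differences in Global Response rates.
- Event counts: the documents give no expected AE rates, so every count below is an assumption. There is no figure in the plan to reproduce, because SAP 3.6 defines no sample size calculation.

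**Formula.** The 95% limits for the risk difference are the values d that solve

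(observed difference − d)² = 1.96² × [p1(1−p1)/n1 + p2(1−p2)/n2] × N/(N−1),

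where N = n1 + n2, and p1 and p2 are the maximum-likelihood rates under the constraint p1 − p2 = d.

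**No events in either arm, 11 per arm.** At the upper limit p2 = 0 and p1 = d, so 11d = c(1−d) with c = 1.96² × 22/21 = 4.024. Then d = 4.024/(11 + 4.024) = 0.268, or ±26.8 points. By symmetry, 11/11 v 11/11 gives the same width, which is relevant if nearly every subject has a TEAE.

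**Five events in each arm, 11 per arm.** At d = 0.392 the constrained rates are p1 = 0.663 and p2 = 0.271. The variance is (0.223 + 0.197)/11 × 22/21 = 0.040, its square root is 0.200, and 0.392/0.200 = 1.96. The limits are ±39.2 points.

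| Assumed events, 11 per arm | Difference (points) | 95% CI (points) |
|---|---|---|
| 0 v 0 | 0 | −26.8 to +26.8 |
| 1 v 1 | 0 | −31.5 to +31.5 |
| 3 v 3 | 0 | −37.1 to +37.1 |
| 5 v 5 | 0 | −39.2 to +39.2 |
| 3 v 1 | +18.2 | about −17 to +51 |
| 5 v 2 | +27.3 | about −13 to +60 |

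At 10 per arm the equal-rate intervals run from ±28.8 (0 v 0) to ±41.0 (5 v 5). At 30 per arm, 0 v 0 gives c = 1.96² × 60/59 = 3.907 and 3.907/33.907 = ±11.5 points. Stopping at 22 therefore widened that interval by a factor of about 2.3 (26.8/11.5).

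**Zero events in one arm.** The exact two-sided 95% upper limit is 1 − 0.025^(1/n): 28.5% at n = 11 and 30.8% at n = 10. An event with a true rate of 10% is missed entirely in an 11-subject arm with probability 0.9^11 = 31%.

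**The mortality interval.** Clopper-Pearson inverts binomial tail probabilities for one proportion. With 3/11 deaths in each arm it gives 6.0% to 61.0% for each arm separately and no interval for the difference. Miettinen-Nurminen gives ±37.1 points for that difference.

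**The case against.** The strongest reply is that descriptive safety reporting is the declared design. The study is exploratory and has no formal sample size, and protocol 19.1 gives its main goal as preliminary effect sizes for the efficacy endpoints. SAP 10.3 matches protocol 19.6.2, so the two documents do not conflict on AE reporting. Counts, percentages and arm sizes will all be shown, so a reader could derive any interval. All of this stands, and it keeps the point minor. It does not close the gap: the primary objective is worded as a comparison, and the same exploratory status did not prevent planned contrasts for biomarkers.

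Two stronger readings are tempting, and the documents support neither.
- A reader might infer that no primary component has a between-arm contrast. Deaths do, in SAP 8.2.3. Its place under efficacy does not remove it, because the ITT and Safety Populations have the same membership rule (SAP 5.2 and 5.3).
- A reader might infer that the plan will present similar percentages as evidence of comparable safety. Neither document plans a safety test, a margin or a conclusion of no difference. That misreading is a risk in how the tables are used, not something the plan proposes.

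It is also fair to say that zero events in both arms is unlikely for TEAEs or deaths. The combination trial cited in protocol 8.1 had six-week mortality of 19.3% and 27.5%, or about 2 to 3 deaths in 11. That weakens 0 v 0 as the lead example, but at 3 v 3 the interval is wider still.

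**Conclusion.** The point holds for TEAEs, drug-related AEs and discontinuations due to AEs: the plan has no between-arm estimate or interval for any of them. For deaths the contrast exists, but its interval cannot be computed by the method named.

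If the observed rates are equal at 11 per arm, true differences of about 27 to 39 points remain compatible with the data over the counts considered. This rests on assumed event counts and on 11 per arm; with 10 per arm the intervals are slightly wider and the conclusion is the same. Severity is minor. No planned result becomes wrong, but the primary comparison would be reported without its uncertainty.

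**What to change.** 1. In the SAP 10.3 overview table, add one column: risk difference (combination minus control) with a Miettinen-Nurminen 95% CI, Safety Population, labelled descriptive. Fill it for TEAEs, treatment-related TEAEs and TEAEs leading to withdrawal of study treatment. These rows are already planned.
2. For deaths, keep a single contrast. Change the SAP 8.2.3 interval from Clopper-Pearson to Miettinen-Nurminen and cross-refer to it from the safety section. Say there that it covers deaths by Day 42 and Day 84, and that later deaths appear only in the TEAE counts.
3. Add a footnote with the exact upper bound for zero events at the actual arm size (28.5% if n = 11), computed from the final numbers. SAP 3.4 (about 11 per group) and SAP 3.7 (about 10 per arm) should be made to agree.

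The cost is one column, one footnote and one method name changed in SAP 8.2.3. No new data, test or power claim is needed.
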